**Study schema:**

**Criteria for Inclusion/Exclusion:**

**Inclusion:** Subjects may be included in the study only if all the following criteria are met:

1. Able and willing to give written informed consent and authorize HIPAA.
2. Patients with migraine with or without aura fulfilling the International Headache Society (IHS) diagnostic criteria 1.1 (migraine without aura) or 1.2.1 (migraine with aura) (International Headache Classification (ICHD)-2004).
3. History of disabling migraine for at least 1 year.
4. MIDAS score  $\geq 11$ .
5. Migraine onset before the age of 50 years.
6. History of 3 – 8 migraine attacks per month ( $< 15$  headache days per month).
7. Male or female, aged 18 years or above.
8. Females of child-bearing potential must be using or willing to use a highly effective form of contraception (e.g. combined oral contraceptive, intrauterine device (IUD), abstinence or vasectomized partner).
9. Able and willing to complete an electronic diary to record details of the migraine attack treated with study drug.

**Exclusion:** Subjects are excluded from the study if any of the following criteria are met:

1. Any medical condition or clinical laboratory test which in the judgment of the Investigator makes the subject unsuitable for the study.
2. Pregnant or breast-feeding women.
3. Women of child-bearing potential not using or not willing to use highly effective contraception.
4. Known hypersensitivity to lasmiditan or to any excipient of lasmiditan oral tablets or any sensitivity to a ditan.
5. History or evidence of hemorrhagic stroke, epilepsy or any other condition placing the subject at increased risk of seizures.
6. History of recurrent dizziness and/or vertigo including benign paroxysmal positional vertigo (BPPV), Meniere's disease, vestibular migraine, and other vestibular disorders.
7. History of diabetes mellitus with complications (diabetic retinopathy, nephropathy or neuropathy).
8. History within the previous three years or current evidence of abuse of any drug, prescription or illicit, or alcohol.
9. History of orthostatic hypotension with syncope.
10. Significant renal or hepatic impairment.
11. Subject is at imminent risk of suicide (positive response to question 4 or 5 on the C-SSRS) or had a suicide attempt within six months prior to the screening visit.
12. Previous participation in this clinical trial.
13. Participation in any clinical trial of an experimental drug or device in the previous 30 days.
14. Known Hepatitis B or C or HIV infection.
15. History, within past 12 months, of chronic migraine or other forms of primary or secondary chronic headache disorder (e.g. hemicranias continua, medication overuse headache) where headache frequency is  $\geq 15$  headache days per month.
16. Use of more than 3 doses per month of either opiates or barbiturates.
17. Initiation of or a change in concomitant medication to reduce the frequency of migraine episodes within three (3) months prior to **Screening/Visit 1**.
18. Subjects who are employees of the sponsor.
19. Relatives of, or staff directly reporting to, the Investigator.

**Criteria for Evaluation:**

**Efficacy/Pharmacodynamics:**

- Headache pain (4 point scale: none (0), mild (1), moderate (2), severe (3))
- Most bothersome symptom (selected from a list of associated symptoms present at predose)
- Nausea, phonophobia or photophobia (yes or no)
- Headache response within 24 hours - time to headache relief and time to pain free
- 24 and 48 hour sustained pain free response
- Presence of vomiting (yes or no)
- Disability (4 point scale: not at all (0), mild interference (1), marked interference (2), completely, needs bed rest (3))
- Requirement for rescue medication between at 2 hours and between 2- 24, and 24-48 hours (yes or no)
- Requirement for recurrence medication between 2- 24, and 24-48 hours (yes or no)
- Patient global impression of change (7 point scale)
- Headache pain after a second dose of lasmiditan for rescue or recurrence of migraine
- Time to headache relief and time to pain free after a second dose of lasmiditan for rescue or recurrence of migraine
- MBS free after a second dose of lasmiditan for rescue or recurrence of migraine

**Safety:**

- Adverse events (spontaneously reported)
- Physical examination
- Vital signs
- 12-lead electrocardiograms
- Clinical laboratory parameters

**Resource utilization:**

- Any CV events in the 6 months prior to screening and/or related resource utilization such as visits to cardiologists, procedures, hospitalizations, new treatments or treatment adjustments for CV disease compared to on study Visit 1 through Visit 2.
- Any visits to an emergency room or physician's office for treatment of migraine in the 3 months prior to screening compared to on study Visit 1 through Visit 2, excluding study specific visits.
- Concomitant medications for the treatment of migraine and/or pain for 3 months prior to screening compared to concomitant medications for migraine and/or pain Visit 1 through Visit 2.
- Missed days of work and/or school.

**Statistical Analysis:**

**Efficacy:**

This multi-center, randomized, double-blind, parallel-group, placebo-controlled clinical study is designed to evaluate the efficacy and safety of lasmiditan 50 mg, of lasmiditan 100 mg and of lasmiditan 200 mg vs. placebo in the acute treatment of migraine based on the first dose. Subjects will be stratified (yes or no) for use of concomitant medications that reduce the frequency of migraine episodes.

Efficacy will be assessed using the primary endpoint of the proportion of subjects headache pain free at 2 hours, defined as moderate or severe headache pain becoming none and the key secondary endpoint of the proportion of subjects MBS free at 2 hours defined as the associated symptoms (nausea, phonophobia or photophobia) present prior to dosing and identified by the subject to be MBS becoming absent.

The primary analyses will compare the proportion of subjects who are headache pain free and the proportion of subjects who are MBS free at 2 hours in the lasmiditan 200 mg and placebo groups in the modified Intent-to-Treat (mITT) population. Each of these two analyses will be carried out using logistic regression Wald Chi-square test with region included in the model and will be conducted using a one-sided test at the  $\alpha=0.025$  level of significance.

If both primary analyses are statistically significant (one-sided,  $p<0.025$ ), additional confirmatory hypotheses will

be tested in the mITT population in the following sequential order:

- Proportion of subjects who are headache pain free at 2 hours in the lasmiditan 100 mg and placebo group.
- Proportion of subjects who are MBS free at 2 hours in the lasmiditan 100 mg and placebo group.
- Proportion of subjects who are headache pain free at 2 hours in the lasmiditan 50 mg and placebo group.
- Proportion of subjects who are MBS free at 2 hours in the lasmiditan 50 mg and placebo group.

All of the above analyses will be completed using one-sided tests at the  $\alpha=0.025$  level of significance. If an analysis is not statistically significant, then all subsequent analyses will be conducted but are designated as exploratory rather than confirmatory.

Additional analyses will explore the time course and effect of the first dose of lasmiditan 200 mg and of lasmiditan 100 mg and of lasmiditan 50 mg on features of migraine including: headache response (a reduction in headache pain from moderate or severe to mild or none), vomiting, disability, headache recurrence and the use of recurrence medication, the use of rescue medication, patient global impression of change, time to headache relief, and time to headache pain free. Descriptive analyses will be performed on the proportion of subjects who are nausea free at 2 hours, the proportion who are phonophobia free 2 hours and the proportion who are photophobia free at 2 hours. Exploratory second dose (for rescue or recurrence of migraine) comparisons between treatment groups will be performed.

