## 10. STATISTICS

Prior to locking and unblinding the database, a detailed statistical analysis plan will be developed before any receipt of study data and decisions will be made regarding the integrity of subject data for inclusion in the statistical analysis. The efficacy analyses and baseline characteristics will be based on the Intent-to-Treat (ITT) and mITT population. The primary analysis will be tested in the mITT population. All safety analyses will be based on the Safety Population. The Per Protocol Population will be used to support the ITT analyses.

All tests of treatment effects will be conducted at a one-sided alpha level of 0.025.

The primary objective of the study is to evaluate the efficacy of lasmiditan versus placebo at 2 hours on migraine headache pain and the MBS as identified by the individual subject based on the first dose.

Summary analysis of the efficacy and safety of the use of a second dose of lasmiditan versus placebo for either rescue or recurrence will be performed only in the subjects that actually took a second dose of study drug within 24 hours of the first dose. Analysis will be performed on the subset of subjects that dosed for rescue and on the subset that dosed for recurrence of migraine.

Data from all investigative sites will be pooled for all planned analyses. Analysis of individual site findings will be considered if necessary. For those measures that are analyzed using change from baseline scores, observed scores may also be presented descriptively.

Any changes in the data analysis methods described in the protocol will require an amendment only if it changes a principal feature of the protocol. Any other changes to the data analysis methods described in the protocol and the justification for making the change will be described in the statistical analysis plan as well as the clinical study report. Additional exploratory analyses will be conducted as deemed appropriate. All data listings, summaries and analyses will be performed by Quintiles.

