#### **10.5.3 Multiplicity Adjustment for Hypothesis Testing**

The gatekeeping procedure will be implemented to prevent Type I error inflation for multiple comparisons among the primary and secondary analyses. The treatment effect between lasmiditan 200 mg and placebo will be tested first for the primary endpoint of the proportion of subjects who are headache pain free and the key secondary endpoint of the proportion of subjects who are MBS free at 2 hours in the mITT population.

If the primary analysis is statistically significant (one-sided,  $p < 0.025$ ), additional confirmatory hypotheses will be tested in the mITT population in the following sequential order:

1. Proportion of subjects who are headache pain free at 2 hours in the lasmiditan 100 mg and placebo group.
2. Proportion of subjects who are MBS free at 2 hours in the lasmiditan 100 mg and placebo group.
3. Proportion of subjects who are headache pain free at 2 hours in the lasmiditan 50 mg and placebo group.
4. Proportion of subjects who are MBS free at 2 hours in the lasmiditan 50 mg and placebo group.

All of the above analyses will be completed using one-sided tests at the  $\alpha=0.025$  level of significance. If one of the analyses is not statistically significant, then all subsequent analyses will be exploratory rather than confirmatory.

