3 EFFICACY AND SAFETY ENDPOINTS

3.1 Primary Efficacy Endpoint

The primary efficacy endpoint is the treatment comparison, between lasmiditan 200 mg and placebo, as measured by subjects who are headache pain-free at 2 hours post first dose.

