11.1 Multiplicity Adjustment

The gatekeeping procedure will be implemented to prevent Type I error inflation for multiple comparisons among the primary and secondary analyses. The primary efficacy endpoint will be tested first. If the primary analysis is statistically significant (one-sided $p < 0.025$), additional confirmatory hypotheses will be tested sequentially, in the following order:

1. Treatment comparison, between lasmiditan 200 mg and placebo, as measured by subjects who

- are MBS-free at 2 hours post-dose.
2. Treatment comparison, between lasmiditan 100 mg and placebo, as measured by subjects who are headache pain-free at 2 hours post-dose.
 3. Treatment comparison, between lasmiditan 100 mg and placebo, as measured by subjects who are MBS-free at 2 hours post-dose.
 4. Treatment comparison, between lasmiditan 50 mg and placebo, as measured by subjects who are headache pain-free at 2 hours post-dose.
 5. Treatment comparison, between lasmiditan 50 mg and placebo, as measured by subjects who are MBS-free at 2 hours post-dose.

If one of the analyses is not statistically significant, then all subsequent analyses will be exploratory rather than confirmatory.

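### Protocol and SAP do not agree, and SAP 5.1 does not say so, on which 200 mg result meets the primary and opens the lower-dose tests

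*Protocol*

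**What the plan says.** **Protocol, Synopsis, Statistical Analysis (Efficacy).** For 200 mg against placebo, with both outcomes taken two hours after dosing: "The primary analyses will compare the proportion of subjects who are headache pain free and the proportion of subjects who are MBS free". The two are tested separately: "Each of these two analyses will be carried out using logistic regression Wald Chi-square test with region included in the model", each at one-sided 0.025, with no order between them. The lower-dose tests carry the condition "If both primary analyses are statistically significant". The preceding paragraph nevertheless names pain-free as the primary endpoint and refers to "the key secondary endpoint of the proportion of subjects MBS free at 2 hours".

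**Protocol 10.5.1 and 10.5.3.** Both 200 mg comparisons are placed in the step tested first, one labelled primary endpoint and the other key secondary endpoint. The gate is then singular: "If the primary analysis is statistically significant". The numbered order in 10.5.3 begins with 100 mg pain-free, so it gives the two 200 mg tests no rank.

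**Protocol section 10, opening text.** "All tests of treatment effects will be conducted at a one-sided alpha level of 0.025". A change to the analysis needs an amendment if it alters a principal feature. Any other change is to be described and justified in the SAP and the study report.

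**SAP 3.1, 3.2 and 11.1.** For the two-hour time point: "The primary efficacy endpoint is the treatment comparison, between lasmiditan 200 mg and placebo, as measured by subjects who are headache pain-free". The 200 mg MBS comparison heads the list of key secondaries. On order: "The primary efficacy endpoint will be tested first", then 200 mg MBS, 100 mg pain-free, 100 mg MBS, 50 mg pain-free and 50 mg MBS, stopping at the first failure.

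**SAP 5.1**, the list of changes and clarifications, does not mention this difference.

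**The concern.** The rule that turns the 200 mg data into a positive or negative primary result should be the same wherever it is written. Here three statements of it can give different answers to two questions. Does pain-free alone meet the primary? Does a failed 200 mg MBS test close the 100 mg and 50 mg tests?

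If 200 mg wins on pain but misses on MBS, the choice of rule would be made with the result in view. A reader of the protocol could argue that the primary objective, which covers both pain and MBS, was not met. A reader of the SAP would say that it was. Under 10.5.3 alone, someone could go on to claim confirmatory status for 100 mg.

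**Working it through.** **1. Reproduce the plan's pain-free power.** Inputs from Protocol 10.1 and SAP 2.2: 7.4% placebo, 18.8% on 200 mg, 570 per arm, one-sided 0.025.

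- Pooled rate = (0.074 + 0.188)/2 = 0.131.
- SE under the null = √(2 × 0.131 × 0.869 / 570) = 0.01999.
- SE under the alternative = √(0.074 × 0.926/570 + 0.188 × 0.812/570) = 0.01970.
- Power = Φ[(0.114 − 1.96 × 0.01999)/0.01970] = Φ(3.80) = 99.99%.

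The same formula gives 92.8% for 100 mg and 94.6% for 50 mg, so the stated figure of more than 90% for each dose reproduces.

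**2. Take the plan's 200 mg MBS power to 570 per arm.** The tables in Protocol 10.1 and SAP 2.2 use 570 for scenario 1, 450 for scenarios 2 and 4, and 575 for scenario 3. The five-seed means agree with the stated 71% and 82.6% to 91%. The simulation cannot be rerun from the documents, so each mean is rescaled by normal approximation with the effect held fixed:

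power at 570 = Φ[(Φ⁻¹(mean) + 1.96) × √(570/n) − 1.96]

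| Scenario | n | Mean power | Calculation | Power at 570 |
|---|---|---|---|---|
| 1 | 570 | 70.9% | none needed | 70.9% |
| 2 | 450 | 85.4% | (1.053 + 1.96) × 1.1255 − 1.96 = 1.431 | 92.4% |
| 3 | 575 | 82.6% | (0.940 + 1.96) × 0.9956 − 1.96 = 0.927 | 82.3% |
| 4 | 450 | 91.0% | (1.341 + 1.96) × 1.1255 − 1.96 = 1.755 | 96.0% |

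**3. Chance of the split result (pain-free passes, MBS fails).** Whatever the correlation between the tests, this lies between 0.9999 − MBS power and 1 − MBS power. It is therefore about 29%, 8%, 18% and 4% for scenarios 1 to 4. Without rescaling, scenarios 2 and 4 would read 15% and 9%, but those belong to 450 per arm. The opposite split (MBS passes, pain-free fails) has a chance below 1 − 0.9999 = 0.01%.

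**4. What each text says in the split result.**

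| Text | Primary met? | 100 mg tests confirmatory? |
|---|---|---|
| Synopsis, read as co-primary | No | No |
| Synopsis, read by endpoint labels | Yes | No |
| Protocol 10.5.3, primary analysis = both 200 mg tests | Unclear | No |
| Protocol 10.5.3, primary analysis = pain-free alone | Yes | Could be read as yes |
| SAP 3.1 and 11.1 | Yes | No |

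**5. Type I error for a 200 mg claim.**

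- Both tests must pass: at most 0.025.
- SAP fixed sequence: 0.025.
- Either test alone counts: 0.05 − P(both reject). With correlation 0 this is 0.05 − 0.0006 = 0.0494; with 0.5, 0.05 − 0.0046 = 0.0454; with 0.9, 0.05 − 0.0148 = 0.0352. The correlation is an assumption, because the documents give none.

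**The case against.** The strongest reply is that the protocol has one primary endpoint. Wherever it classifies the two, pain-free is primary and MBS is key secondary, and the SAP follows those labels. The SAP describes itself as specifying the protocol's methods, and placing a primary ahead of a key secondary could be called specification. The synopsis and SAP 11.1 also close the lower-dose tests under the same condition. The protocol nowhere says that a missed MBS test means the primary has failed. Finally, the last sentence of 10.5.3 makes everything after a failed test exploratory, which closes the 100 mg gate if 200 mg MBS is counted among those tests.

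Much of this stands. The labels favour the SAP's reading, and the conflict lies partly inside the protocol. The labels do not settle it, though. The primary objective covers both pain and MBS, and the synopsis calls both comparisons primary analyses and requires both. Section 10.5.3 does not say whether its singular primary analysis includes MBS.

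A reader might go further and infer that the protocol sets up two separate primaries, each claimable at 0.025, with family-wise error of about 0.035 to 0.049. The documents do not support that. No passage lets either test alone count as success, the synopsis asks for both, and 10.5.3 says the procedure is there to prevent inflation. The missing order fails to exclude that reading, but it does not establish it.

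**Conclusion.** The inconsistency is real and undeclared. Under the planning assumptions it matters in a result with a chance of about 4% to 29% at 570 per arm, depending on the MBS scenario; 29% is the scenario the plan calls most conservative. In that result the documents can disagree on whether the primary is met and, on one reading of 10.5.3, on whether 100 mg may be tested as confirmatory. The reverse split is negligible on the same assumptions.

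This is a defect in the stated decision rule. It does not show an inflated error rate: that rate is at or below 0.025 under the SAP sequence and under a rule that both must pass. The probabilities rest on the Phase 2 rates, on the plan's simulated MBS powers taken as given, and on a normal-approximation rescaling for scenarios 2 to 4.

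**What to change.** Before unblinding, state one rule in the protocol synopsis, Protocol 10.5.1 and 10.5.3, and the SAP.

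- **Simplest: the SAP 11.1 sequence.** The order is 200 mg pain-free as the single primary analysis, then 200 mg MBS, 100 mg pain-free, 100 mg MBS, 50 mg pain-free and 50 mg MBS, each at one-sided 0.025 and each confirmatory only if all before it succeeded. This is fully ordered and matches the protocol's endpoint labels. Replace the plural primary analyses and the both-condition in the synopsis, number the two 200 mg tests in 10.5.3, and record in SAP 5.1 that the sequence supersedes the synopsis wording.
- **If co-primaries are intended.** Say that both 200 mg tests must pass for the primary to be met, and align the SAP and the endpoint labels. The power to quote for 200 mg is then the joint figure, about 71% in scenario 1, in place of the more than 90% for pain-free alone.

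Under the protocol's own section 10, the sponsor should also record whether this is a principal feature that needs an amendment or a change to be justified in the SAP. Either route costs a few sentences and no new data or patients.

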#### **Sample Size Rationale**

This Phase 3 study is designed to demonstrate that lasmiditan is effective in the treatment of acute migraine in adult patients with and without aura. The sample size was estimated based on the 2 hour headache pain free and associated symptoms (nausea, phonophobia, or photophobia) free response rates observed in the Phase 2 study [COL MIG-202](#).

Dose	Pain free	Nausea free	Phonophobia free	Photophobia free
Placebo	7.4%	59.3%	51.9%	34.6%
50 mg	13.9%	68.4%	58.2%	53.2%
100 mg	13.6%	74.1%	75.3%	67.9%
200 mg	18.8%	63.8%	59.4%	58.0%

For the primary endpoint of the proportion of patients pain free at 2 hours a sample size of 570 evaluable subjects per arm provides power of >90% for the 50 mg dose, the 100 mg dose and the 200 mg dose.

In order to estimate sample size for the key secondary endpoint of proportion of patients MBS free at 2 hours, simulation was performed in SAS on the conditional probability of being free from any one symptom defined as MBS under 4 different scenarios. For each symptom or combination of symptoms, the likelihood of an individual symptom being the MBS was estimated. In the most conservative scenario (scenario 1) it was assumed that nausea would always be declared the MBS if it was present, regardless of the presence of other symptoms (phonophobia or photophobia). The other 3 scenarios assumed lower likelihoods of nausea to be considered the MBS and allowed for the other symptoms (either phonophobia or photophobia) to be considered the MBS at a higher rate. This resulted in power estimates of > 95% for MBS at a sample size of 570 for the lasmiditan 50 mg dose and >99% for MBS at sample sizes of 450 to 570 per arm for the 100 mg dose across all 4 scenarios. For the 200 mg dose, an average power of 71% was estimated across five seeds under the most conservative scenario 1. In contrast, the 3 scenarios that did not declare nausea to be the default MBS if it was present estimated a greater average power of 82.6% to 91%.

Group	Scenario	Variable	Seed				
			55405	74951	82002	82377	90075
Placebo vs D50	1	Power (MBS)	96.90%	95.90%	96.10%	95.60%	96.80%
		Sample Size	570	570	570	570	570
	2	Power	93.70%	94.30%	94.80%	93.90%	93.90%
		Sample Size	450	450	450	450	450
	3	Power	90.40%	90.40%	90.10%	91.00%	91.40%
		Sample Size	575	575	575	575	575
	4	Power	93.70%	94.30%	94.80%	93.90%	93.90%
		Sample Size	450	450	450	450	450
Placebo vs D100	1	Power (MBS)	>99.99%	>99.99%	>99.99%	>99.99%	>99.99%
		Sample Size	570	570	570	570	570
	2	Power	99.90%	>99.99%	>99.99%	>99.99%	>99.99%
		Sample Size	450	450	450	450	450
	3	Power	>99.99%	>99.99%	>99.99%	>99.99%	>99.99%
		Sample Size	575	575	575	575	575
	4	Power	99.90%	>99.99%	>99.99%	>99.99%	>99.99%
		Sample Size	450	450	450	450	450
Placebo vs D200	1	Power	70.87%	70.87%	72.97%	71.17%	68.47%
		Sample Size	570	570	570	570	570
	2	Power	84.40%	85.00%	85.80%	85.90%	85.80%
		Sample Size	450	450	450	450	450
	3	Power	83.50%	83.20%	81.30%	83.40%	81.80%
		Sample Size	575	575	575	575	575
	4	Power	90.20%	90.50%	92.50%	91.40%	90.40%
		Sample Size	450	450	450	450	450

 Mean rate is the freedom from MBS at 2 hours post dose.

P=placebo, L = lasmiditan

It is expected for a one-sided, two-sample comparison of proportions at the 2.5% level of significance, a sample size of 570 subjects per treatment arm (as defined by the first dose) provides >90% power to detect a difference in headache pain free response rates for assumed true rates of 7.4% and 18.8% (placebo and 200 mg), 7.4% and 13.6% (placebo and 100 mg) and 7.4% and 13.9% (placebo and 50 mg) >90 % power for MBS for both the 50 mg dose arm and the 100 mg dose arm and very near or higher than 80% power for MBS in the 200 mg dose arm.

